7.2 Objectives

The concept of evaluation of the effectiveness of RM plans is defined by EU guidance: Module XVI⁽¹⁾ and Module XVI B.B11.4⁽¹⁾.

Effectiveness, for the purposes of this study, is defined as a combination of effective distribution, usage, knowledge, and adoption of appropriate stakeholder behaviours by HCPs, patients and caregivers.

The objectives of the survey are to evaluate the effectiveness of $ABILIFY^{\circledast}$ RM tools in markets where the adolescent bipolar I mania indication has been approved, and where $ABILIFY^{\circledast}$ has subsequently been prescribed in this indication for at least 6 months.

The surveys will provide information from HCPs (see Annex 1), and patients (see Annex 2) and caregivers (see Annex 3) on:

- 1. Distribution of the RM tools
- 2. Awareness and usage of the RM tools
- 3. Knowledge and comprehension of the key important identified risks
- 4. Behavioural responses to hypothetical risk scenarios
- 5. Minimisation of inappropriate starting dose and patient age

The evaluation is planned to be performed 12 months after implementation of the educational measures, in up to 13 EU member states (where usage of aripiprazole in paediatric patients is highest), to allow sufficient time for use and experience of the materials to conduct a meaningful assessment.

7.2.1 Primary Objectives

The five-level RM evaluation model, shown in Figure 1, developed by Pope Woodhead, describes how effectiveness can be measured at different levels. This has been used to determine the primary objectives for the study; which will investigate the first four of these (distribution, awareness and utilisation, risk knowledge and comprehension and behaviours). The primary objectives are:

- 1. Evaluation of RM tool awareness and effective distribution (see Figure 1; levels 1 and 2): To determine the proportion of HCPs that are aware of the existence of the RM tools and how the tools were accessed (i.e. paper or electronic versions).
- 2. Evaluation of RM tool utilisation (see Figure 1; level 2):

 To determine who uses the RM communication tools, how, when they are used and how often they are used.
- 3. Evaluation of risk knowledge and comprehension (see Figure 1; level 3):

 To determine the level of knowledge and comprehension of the key risks associated with ABILIFY® when used for the treatment of adolescent bipolar I mania. The responses of HCPs and patients / caregivers will be evaluated according to their:
 - a. Knowledge of indicated age range, indicated dosage (HCPs only), and duration of treatment
 - b. Knowledge / understanding of important safety and tolerability information
 - c. Knowledge / understanding of those symptoms that require immediate contact with the treating HCP (patients / caregivers only)
 - d. Knowledge to respond appropriately to hypothetical risk scenarios (HCPs) and more simple information about identified risks (patients / caregivers)

[figure not shown]

Figure 1: Five-Level Model for Risk Minimisation Evaluation

4. Evaluation of behaviour (see Figure 1; level 4):

To evaluate HCP and patient behaviours using behavioural questions and scenarios, certain desired behaviours of HCPs and patients / caregivers will be evaluated through responses to behavioural questions as follows:

- a. Do HCPs review safety information with their patients / caregivers?
- b. Do HCPs distribute the patient information brochure to their patients / caregivers?
- c. Do HCPs educate patients / caregivers about symptoms of ADRs of concern (i.e. extrapyramidal symptoms, weight gain, somnolence, and fatigue), and about the need to report these ADRs immediately to the treating physician?
- d. Would patients / caregivers immediately notify their treating physician of the potential ADRs of concern (i.e. extrapyramidal symptoms, weight gain, somnolence, and fatigue)?

The results of this study will also be used to assess if the RM tools on the real-world risks that the tools have been designed to minimise especially that the maximum starting dose of ABILIFY® for the adolescent bipolar I mania indication is not exceeded, and that the minimum age of patients receiving ABILIFY® for the bipolar I mania indication is not breached. This will be achieved by including in the HCP questionnaire the usual starting dose of ABILIFY® used in the adolescent indication, identifying the appropriate dose and the minimum age of the patient when the drug is prescribed, as well as the actual ages of patients doing the patient/carer questionnaire.

Date: October 15th, 2013

ABILIFY®

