A reference document provided to HCPs for distribution to their patients / caregivers outlining the treatment of adolescent bipolar I mania with ABILIFY, including advice on being vigilant for adverse drug reactions (ADRs) and contacting their treating physician immediately if signs of ADRs are suspected. Overall, the Patient brochure is designed to educate patients and carers on how to take ABILIFY®, to be vigilant for ADRs and report

immediately.

The key risks minimised by these RM tools are:

- Weight gain
- Extrapyramidal symptoms (EPS)
- Fatigue, and
- Somnolence

Another critical aspect of the risk minimisation education is to ensure that that maximum recommended dose is not exceeded and the minimum age of patients is not breached and the effectiveness evaluation survey will collect specific data to evaluate knowledge and prescribing behaviours for age and dose.

The tools clearly state the importance of being vigilant for the ADRs of concern and reporting them immediately, should they arise.

The RM tools also cover the contraindications and other common side-effects that are described in the product labelling. Further to this, the tools discuss how treatment should be initiated and titrated, that the treatment regimen should only be altered, or discontinued, by the prescriber. The EU-RMP committed Otsuka Pharmaceutical Europe Ltd., as the marketing authorisation holder (MAH), to evaluate the effectiveness of these additional RM activities for the adolescent bipolar I mania indication. This protocol describes the method for the HCP and Patient / Caregiver surveys that will be used to evaluate the effectiveness of these RM tools defined as a combination of effective distribution, usage, knowledge and adoption of appropriate stakeholder behaviours.

It should be noted that, for the duration of the surveys described in this protocol, Bristol-Myers Squibb (BMS) will retain responsibility for pharmacovigilance until Otsuka takes over responsibility for pharmacovigilance for ABILIFY[®] (mid 2016). Otsuka (the MAH) and Lundbeck affiliates (alliance partners in some markets participating in the survey) will be responsible for the operational aspects of implementing the surveys.

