- 1. To determine the proportion of HCPs, patients and caregivers that are aware of the existence of the RM communication tools and how these tools were accessed (i.e. paper or electronic versions).
- 2. To determine who uses the RM communication tools, and how, when and how often they are used.
- 3. To determine the level of knowledge and comprehension of the key elements of identified risks of concern associated with ABILIFY® for the adolescent bipolar I mania indication (i.e. EPS, weight gain, somnolence and fatigue).
- 4. To assess the effect of the tools on the real-world risks that the educational tools have been designed to minimise, namely the maximum starting dose of ABILIFY® for the adolescent bipolar I mania indication is not exceeded, and the minimum age of patients receiving ABILIFY® for the adolescent bipolar I mania indication is not breached.
- 5. To evaluate the HCP, patient and caregiver behaviours via behavioural questions and scenarios.

The following tables illustrate which components of the surveys will be used to carry out these evaluations:

Table 1: Demographic questions

Annex	Questions examining participant demographics
Annex 1: HCP survey	1 to 4
Annex 2: Patient survey	1 to 3
Annex 3: Caregiver survey	1 to 3

Table 2: Understanding RM tool awareness and distribution

Annex	Questions designed to understand RM tool awareness
	and distribution
Annex 1: HCP survey	7, 8, 15, 16
Annex 2: Patient survey	4, 5
Annex 3: Caregiver survey	4, 5

ABILIFY®

Table 3: Understanding RM tool use and utility

Annex	Questions designed to understand tool use and	
	utility	
Annex 1: HCP survey	9 to 14, and 17 to 23	
Annex 2: Patient survey	6 to 11	
Annex 3: Caregiver survey	6 to 13	

For this survey, the intention is to primarily test knowledge indirectly, as meeting behavioural goals will require some degree of working-knowledge of ABILIFY[®] benefits and risk, when used for the adolescent bipolar I mania indication.

Tables 4 and 5 contain the questions that reflect understanding of how to take ABILIFY[®], how to treat ADRs (HCPs), and awareness of risks and what to do if risks are identified (patients / caregivers).

Table 4: Understanding knowledge of RM tool content

Annex	Questions designed to understand knowledge of tool	
	content	
Annex 1: HCP survey	24 – 35	
Annex 2: Patient survey	12 – 33	
Annex 3: Caregiver survey	14 – 35	

Table 5: Knowledge of potential or identified risks of concern

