Identified or potential	Question item in	Question item in Patient /
risk of concern	HCP survey	Caregiver survey
Age range	4	(Note that age of patients will be
		collected as a demographic (Q2).
		This may indirectly help to
		understand if ABILIFY® is
		prescribed to appropriate patients
		in this indication.)
Dose	5	Indirectly 12 -17 (Patients), 14-19
	Case Studies 1 (24) 2	(Caregivers)
	(25) and 3 (28)	
Duration of treatment	Case studies 3 (29)	Indirectly 3
	and 4 (31-33)	
Extrapyramidal symptoms	30	24 – 26 / 26 – 28
(EPS)		

Weight gain	26, 34, 35	19 – 23 / 21 – 25
Somnolence	32	30 – 32 / 32 – 34
Fatigue	31, 33	27 – 29 / 29 – 31

Table 6: Understanding behaviours

Appendix	Questions designed to understand behaviours
Appendix 1: HCP survey	Case studies
Appendix 2: Patient survey	23, 26, 29, 32
Appendix 3: Caregiver survey	25, 28, 31, 34

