8.3 Variables

Variables of interest and their definition include:

• Age of patient

Defined as the age of the patient at treatment initiation

Dose

Defined as the most recent dose taken before completing the survey

• Treatment duration

Defined as the length of time since the first dose taken for this indication, irrespective of whether treatment is continuous or interrupted

• HCPs' experience using ABILIFY® for the adolescent bipolar I mania indication
Defined as how many the HCP has treated with ABILIFY® for moderate to severe manic
episodes in bipolar I disorder in adolescents aged 13 years and older

• Usage of tools

Defined as whether the respondent has used the RM tools on one or more occasions

• Medical specialty

Defined as: psychiatrist, child / adolescent psychiatrist, nurse or prescriber

• Country

Country where the HCP or patient / caregiver resides

The key survey effectiveness evaluation metrics are shown in Table 7. Questions designed to measure: demographics, awareness and distribution, use and utility, knowledge of tool content, knowledge of identified or potential risks of concern and behaviours are described in Section 9.1.1.

ABILIFY®

Table 7: Key effectiveness evaluation metrics

_	Target Audience	
Metrics	НСР	Patient / Caregiver
Awareness of tools	X	X
Utilisation of tools	X	X
Knowledge and comprehension		
Symptoms requiring physician notification	X	X
Recommended age	X	N/A
Indicated dose	X	N/A
Indicated treatment duration	X	X
Risks of		
• EPS	X	X
 Weight gain 	X	X
 Somnolence 	X	X
• Fatigue	X	X
Ability to respond correctly to hypothetical	X	X
risk scenarios		
Behaviour		
Reviewing safety information with	X	
Patients / Caregivers		
Monitor for ARs and appropriate action if	X	
ADR is identified		
Distribution of Patient information	X	X
brochure to Patients / Caregivers		
Educating Patients / caregivers about	X	X
symptoms of EPS, weight gain,		
somnolence and fatigue and need to report		
them to a physician		

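### Primary endpoint 4 asks whether the maximum starting dose is exceeded in practice, but the stated measure is the HCP's self-reported usual starting dose, which misses occasional breaches

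*Protocol*

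**What the plan says.** Section 8.1 lists as primary endpoint 4 the effect of the tools on real-world risks, "namely the maximum starting dose of ABILIFY® for the adolescent bipolar I mania indication is not exceeded", together with the corresponding limit on minimum age. Section 6 calls these limits a critical part of the education and says the survey "will collect specific data to evaluate knowledge and prescribing behaviours for age and dose".

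The method is given twice, in objective 5 of the front-page table and at the end of section 7.2.1: "This will be achieved by including in the HCP questionnaire the usual starting dose of ABILIFY® used in the adolescent indication". The sentence goes on to "identifying the appropriate dose and the minimum age of the patient when the drug is prescribed, as well as the actual ages of patients" taking part in the patient/carer survey.

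The other visible dose material is:
- Section 8.3 on the dose variable: "Defined as the most recent dose taken before completing the survey".
- Table 5, HCP survey: question 5 (wording withheld) and case-study items 24, 25 and 28.
- Table 5, patient/caregiver survey: "Indirectly 12 -17 (Patients), 14-19" for caregivers.
- Table 7: indicated dose is an HCP metric and is marked not applicable for patients and caregivers.

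For age, section 8.2.2 says question 2 of the patient/carer survey asks how old the patient was when treatment began.

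**The concern.** Whether a maximum was exceeded depends on the individual starts above it. A usual dose summarises the middle or most common part of an HCP's practice and drops those starts. For HCPs who mostly comply, the error runs one way only, towards no exceedance.

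This matters because starting dose is one of the two real-world limits named in endpoint 4. Sections 3.2 and 6 say the results go to the EMA and may lead to changes in the EU-RMP. A reassuring dose result that partly reflects the form of the question would feed into that decision. No later analysis can recover starting doses that were not collected.

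**Working it through.** **Figures in the plan.** The protocol gives no figure for starting-dose breaches. Its worked precision figure (section 8.5, UK) reproduces: 1.96 × √(0.85 × 0.15 / 13) × √((2188 − 13) / (2188 − 1)) = 19.36%. That is sampling error for a knowledge question. It says nothing about what the dose item measures, and a larger sample would not remove the bias.

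**Does any visible item record actual starting doses?**
- Usual starting dose (section 7.2.1): real practice, but a typical value.
- Identifying the appropriate dose (same sentence): reads as knowledge.
- HCP items 24, 25 and 28: case studies, which section 8.1 describes as hypothetical scenarios.
- Patient and caregiver dose items: indirect by the protocol's own label.
- Dose variable (section 8.3): the most recent dose, not the starting dose.
- Age: age at initiation is asked for each surveyed patient or through the caregiver.

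So the age limit has a patient-level measure and the starting-dose limit has none described.

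**Illustration only.** The inputs m and q are assumptions. Each HCP has m starts, each above the limit independently with the same probability q, and the usual dose is in breach only when more than half of the starts are.
- P(at least one breach) = 1 − (1 − q)^m
- P(usual dose in breach) = P(X > m/2), with X ~ Binomial(m, q)

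For m = 5 and q = 10%:
- At least one breach: 1 − 0.9⁵ = 41.0%
- Usual dose in breach: 10(0.1)³(0.9)² + 5(0.1)⁴(0.9) + (0.1)⁵ = 0.86%

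Range:
- m = 1: both equal q, so nothing is hidden.
- m = 5, q from 5% to 30%: at least one breach 22.6% to 83.2% of HCPs; usual dose in breach 0.1% to 16.3%.
- m = 10, q from 5% to 30%: at least one breach 40.1% to 97.2%; usual dose in breach under 0.01% to 4.7%.

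The country quotas sum to 6 × 13 + 6 × 12 = 150 HCPs. At m = 5 and q = 10%, that is about 61 HCPs with a breach and about 1.3 whose usual dose shows it. The 150 may include nurses and pharmacists, so the percentages are the safer reading.

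The result also depends on how breaches are spread. If 10% of HCPs always exceeded the limit, the rest never did, and volumes were equal, then 10% of starts would breach and 10% of HCPs would report it, with no gap. The gap therefore runs from nothing to nearly everything, depending on inputs the documents do not give.

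**The case against.** **The HCP questionnaire is withheld.** This stands as a limit on certainty. The wording of question 5 is not visible, question 6 appears in none of Tables 1 to 6, and section 8.1 says the web format allows follow-on questions. A reader might infer that prescribers are asked nothing about actual starting doses except the usual one. The documents do not support that. They support a narrower statement: the protocol's own account of how the endpoint will be met, given twice, names the usual dose and no actual starting doses.

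**Usual practice is a reasonable target for an education survey.** This stands in part. Systematic misunderstanding would show as a usual dose above the limit and would be caught. But the endpoint is worded as a real-world maximum not being exceeded, which is a different claim.

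**The limitation is disclosed.** Section 8.6 says behaviour is evaluated indirectly and that tool use is not related to actual outcomes. That is a general caveat. It does not say that occasional dose breaches go unseen, and endpoint 4 keeps its wording.

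**HCPs may have very few such patients.** Section 8.2.2 expects a small pool of treating HCPs, but patients treated per HCP is not given. With one start each the problem disappears. Low volume would also make actual starting doses easier to recall.

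**Conclusion.** The endpoint and its stated measure do not match. As described, HCPs who usually comply but occasionally exceed the maximum starting dose would be recorded as compliant, so the result is biased towards no exceedance. Habitual breaches are still detected.

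The size cannot be derived from the documents, and the percentages above are illustrations. A reader might also infer a ceiling, that a compliant usual dose means fewer than half of starts breach. That fails if usual means most common: with 40% of starts at a compliant dose and 30% at each of two higher doses, the most common dose complies while 60% of starts breach.

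The conclusion rests on the visible method statements and would need revisiting if the withheld questionnaire does collect actual starting doses. No view is taken on which dose is correct.

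**What to change.** Before the survey content is finalised (Q1 2014 in section 5):
- Have the HCP dose item, objective 5 and the matching sentence in section 7.2.1 collect the starting dose in each of the HCP's last few adolescent patients started since receiving the tools.
- Report the proportion of those starts above the labelled maximum, with an interval that allows for clustering by HCP.
- Keep usual starting dose as a descriptive item.

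A highest-ever dose, or a count of HCPs with at least one breach, is less suitable. The first could include starts made before the tools arrived. The second rises with volume: at the same 10% breach rate the illustration gives 41% of HCPs with 5 starts and 65% with 10.

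If the item cannot be changed, restate endpoint 4 as self-reported usual starting dose and do not conclude that the maximum was not exceeded. If the withheld questionnaire already records actual starting doses, the method statements should say so.

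The cost is one reworked item, the matching protocol sentences, slightly more respondent time, some recall error and a possibly less favourable figure.

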8 RESEARCH METHODS

8.1 Study Design

This study is a non-interventional, observational, cross-sectional study comprising three sets of web-based surveys to examine the effectiveness of the RM materials used to educate HCPs, patients and caregivers on the appropriate use of ABILIFY® for the adolescent bipolar I mania indication.

Each survey (for HCPs or Patients / Caregivers) will have two parts:

- 1. A structured questionnaire (predominantly multiple-choice answers) to test participants' awareness of tools and to gather evaluation metrics related to the utility, use and understanding of tool content and messages designed to educate HCPs and educate patients / caregivers either via their HCP(s) or from the PCIB.
- 2. Hypothetical scenarios are presented to ascertain whether the education provided by the tools influences the user's behaviour in an appropriate way.

Web-based surveys have been selected as the appropriate research approach because:

- 1. The surveys include an assessment of behaviours using interactive scenarios that are difficult to implement by other means. Question navigation in scenarios, and the survey as a whole, also provides information about survey participants' behaviours (e.g. revising answers), which is not possible to collect through other means.
- 2. HCPs and patients are likely to be familiar with internet-based technologies; more than 40% of hospitals in Western Europe are now non-paper based a proportion that is growing each year ⁽³⁾.
- 3. Web-based surveys can be answered at the participant's convenience and means that the participant does not have to arrange to be interviewed this can increase participants' motivation to take part in the survey, thereby potentially improving response rates.
- 4. Web-based surveys ask standardised questions and will, therefore, elicit more consistent and reliable results ⁽⁴⁾ compared with telephone based interviews⁽⁵⁾.
- 5. Web-based techniques allow for interactivity to be introduced into the survey; e.g. logic to ask follow-on or not ask irrelevant questions and ability for users to go back and change answers if they have reconsidered their answers which can strengthen behavioural surveys

The surveys are not intended as a mechanism for the collection of ADRs, they are designed to understand HCPs' and patients' awareness, utilisation, knowledge of ADRs of concern and behaviours (via scenarios).

ABILIFY[®]

Primary endpoints

The primary endpoints are:

- 1. To determine the proportion of HCPs, patients and caregivers that are aware of the existence of the RM communication tools and how these tools were accessed (i.e. paper or electronic versions).
- 2. To determine who uses the RM communication tools, and how, when and how often they are used.
- 3. To determine the level of knowledge and comprehension of the key elements of identified risks of concern associated with ABILIFY® for the adolescent bipolar I mania indication (i.e. EPS, weight gain, somnolence and fatigue).
- 4. To assess the effect of the tools on the real-world risks that the educational tools have been designed to minimise, namely the maximum starting dose of ABILIFY® for the adolescent bipolar I mania indication is not exceeded, and the minimum age of patients receiving ABILIFY® for the adolescent bipolar I mania indication is not breached.
- 5. To evaluate the HCP, patient and caregiver behaviours via behavioural questions and scenarios.

The following tables illustrate which components of the surveys will be used to carry out these evaluations:

Table 1: Demographic questions

Annex	Questions examining participant demographics
Annex 1: HCP survey	1 to 4
Annex 2: Patient survey	1 to 3
Annex 3: Caregiver survey	1 to 3

Table 2: Understanding RM tool awareness and distribution

Annex	Questions designed to understand RM tool awareness
	and distribution
Annex 1: HCP survey	7, 8, 15, 16
Annex 2: Patient survey	4, 5
Annex 3: Caregiver survey	4, 5

ABILIFY®

Table 3: Understanding RM tool use and utility

Annex	Questions designed to understand tool use and	
	utility	
Annex 1: HCP survey	9 to 14, and 17 to 23	
Annex 2: Patient survey	6 to 11	
Annex 3: Caregiver survey	6 to 13	

For this survey, the intention is to primarily test knowledge indirectly, as meeting behavioural goals will require some degree of working-knowledge of ABILIFY[®] benefits and risk, when used for the adolescent bipolar I mania indication.

Tables 4 and 5 contain the questions that reflect understanding of how to take ABILIFY[®], how to treat ADRs (HCPs), and awareness of risks and what to do if risks are identified (patients / caregivers).

Table 4: Understanding knowledge of RM tool content

Annex	Questions designed to understand knowledge of tool	
	content	
Annex 1: HCP survey	24 – 35	
Annex 2: Patient survey	12 – 33	
Annex 3: Caregiver survey	14 – 35	

Table 5: Knowledge of potential or identified risks of concern

Identified or potential	Question item in	Question item in Patient /
risk of concern	HCP survey	Caregiver survey
Age range	4	(Note that age of patients will be
		collected as a demographic (Q2).
		This may indirectly help to
		understand if ABILIFY® is
		prescribed to appropriate patients
		in this indication.)
Dose	5	Indirectly 12 -17 (Patients), 14-19
	Case Studies 1 (24) 2	(Caregivers)
	(25) and 3 (28)	
Duration of treatment	Case studies 3 (29)	Indirectly 3
	and 4 (31-33)	
Extrapyramidal symptoms	30	24 – 26 / 26 – 28
(EPS)		

Weight gain	26, 34, 35	19 – 23 / 21 – 25
Somnolence	32	30 – 32 / 32 – 34
Fatigue	31, 33	27 – 29 / 29 – 31

Table 6: Understanding behaviours

Appendix	Questions designed to understand behaviours
Appendix 1: HCP survey	Case studies
Appendix 2: Patient survey	23, 26, 29, 32
Appendix 3: Caregiver survey	25, 28, 31, 34

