8.6 Limitations of the Research Methods

Limitations include:

- Sampling bias of HCPs and patients (although measures are being put in place to minimise this).
- Participation bias (HCPs and patients or caregivers who volunteer to take part might be more likely to be interested in the product and RM), sampling will minimise bias owing to differential participation of different HCP types.

- Behaviour is being indirectly evaluated (as distinct from real-world behaviour).
- Survey is not relating use of tools to actual outcomes.
- It is not possible (for both ethical and practical reasons) to introduce a control (no exposure to RM tool) group, as RM tools must be universally offered in all countries as part of market authorisation.
- The level of education provided by different HCPs to patients / caregivers will affect how these answer survey questions it will not be possible to stratify patient / carer responses by HCP type (e.g. some child psychiatrists may provide excellent education whilst others do not). The survey will not link the patient / carer to their HCP.
- Social desirability bias (SDB), although potentially present in sample questionnaire
 studies, will be limited by avoiding direct interviewer questionnaires, by wording the
 introduction to emphasise that there are no "correct" answers, the measurement of
 behavioural choice rather than simply thinking, and also wording pre-ambles and
 question stems appropriately, to avoid any risk of inference as to "desirable" response.

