9.1.2 Informed Consent

As part of the recruitment process, HCPs will be asked to encourage patients and carers to participate in the patient and carer surveys. HCPs will be given letters to give to the Patient / carer that contain an informed consent section. This section describes:

- 1. Why patients / carers are being invited,
- 2. What the survey aims to ascertain,
- 3. The duration of the survey,
- 4. How the data will be aggregated and anonymised, and
- 5. How personal data will be respected and protected (and how survey participants' identities will be protected through the use of unique identifiers).

Since the indicated patients are adolescents (aged between 13 and 17), parental / guardian consent will be required before patients are surveyed.

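### Primary endpoint 4 promises an effect of the tools on real-world dose and age breaches that this design cannot estimate; its age data probably under-capture breaches, and 8.3 does not define starting dose.

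*Protocol*

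**What the plan says.** - **Endpoint.** Protocol 8.1, primary endpoint 4: "To assess the effect of the tools on the real-world risks that the educational tools have been designed to minimise". The risks named are exceeding the maximum starting dose and breaching the minimum age. Objective 5 in the front-page table matches it. Section 7.2.1 carries the same aim.
- **Design.** Protocol 8.1: "This study is a non-interventional, observational, cross-sectional study comprising three sets of web-based surveys". Sections 3.2 and 6 say the results will establish baseline levels of usage, knowledge and behaviour.
- **Limitations.** Protocol 8.6: "It is not possible (for both ethical and practical reasons) to introduce a control (no exposure to RM tool) group", and "Survey is not relating use of tools to actual outcomes". The same list says that behaviour is measured only indirectly, and that patient and caregiver answers are not tied back to the HCP.
- **Age and dose sources.** Section 7.2.1 takes the usual starting dose and the minimum age at prescribing from the HCP questionnaire, "as well as the actual ages of patients doing the patient/carer questionnaire". Section 8.2.2 says that Question 2 of the patient/carer survey asks age at treatment initiation.
- **Who can enter.** Section 8.2.2 admits HCPs caring for paediatric bipolar I mania patients who receive the drug. Section 8.2.4 excludes HCPs only. Section 9.1.2 reads: "Since the indicated patients are adolescents (aged between 13 and 17), parental / guardian consent will be required before patients are surveyed". Section 8.3 defines HCP experience by patients treated for manic "episodes in bipolar I disorder in adolescents aged 13 years and older".
- **Dose variable.** Section 8.3 defines dose as the latest one taken before the survey is completed.

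**The concern.** An effect is a difference between what happened with the tools and what would have happened without them. The protocol offers no observation of the second state, yet a primary endpoint is worded as if it did. The results go to the EMA and may lead to changes in the risk management plan (3.2, 6). A low breach count under this endpoint could therefore be reported as evidence that the tools worked. The age and dose inputs add to the problem. The age data come partly from patients whom HCPs choose to list under an indication that starts at 13, and the only dose variable defined in 8.3 is not the dose named in the endpoint.

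**Working it through.** **1. The plan's own figure.** Inputs from 8.5: n = 13 HCPs, N = 2188 (UK), 85% correct, 95% confidence.

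Margin = 1.96 × √[0.85 × 0.15 / 13 × (2188 − 13)/(2188 − 1)] = 19.36%.

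This agrees with the stated value (19.41% without the finite-population term). It is the precision of one proportion. Section 8.5 gives no breach rate, contrast or power for endpoint 4.

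**2. Is there any comparator?** There are three candidates:
- *Unexposed control:* ruled out in 8.6.
- *Pre-tool or historical reference:* none. Sections 3.2 and 6 make this survey the baseline.
- *Users against non-users (3.9):* a descriptive, self-selected split. Because patients are not linked to their HCP, a patient's age at initiation cannot be related to whether the prescriber used the HCP brochure.

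The split is also weak on size. The documents do not give the shares, so these are assumptions: 150 HCPs (6 × 13 + 6 × 12, table in 8.5), 85% correct among users and 70% among non-users, a 15-point gap. The formula is

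power = Φ{[0.15 − 1.96 √(p̄(1 − p̄)(1/n₁ + 1/n₂))] / √(0.70 × 0.30/n₁ + 0.85 × 0.15/n₂)},

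with p̄ the weighted mean, n₁ the non-users and n₂ the users.

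| Non-users | n₁ / n₂ | Power |
|---|---|---|
| 50% | 75 / 75 | 60% |
| 20% | 30 / 120 | 48% |
| 10% | 15 / 135 | 35% |

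This illustrates a knowledge item. Even high power would leave the contrast confounded.

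**3. What a zero age count would mean.** The exact 95% upper limit for 0 of n is 1 − 0.025^(1/n).
- n = 150 patient/caregiver respondents: 2.4%
- n = 13 (one larger country): 24.7%
- n = 12 (one smaller country): 26.5%

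Let π be the true share of patients under 13 at initiation, and r the chance that such a patient is listed and takes part, relative to one aged 13 or over. The survey estimates q = rπ / (1 − π + rπ). If r < 1, then q < π. Only r = 0 forces q to zero. The 2.4% bounds q, and it bounds π only if r = 1.

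**4. Where does r stand?** *Pulling it below 1:* the indication is 13 and older (3.2, 6), the consent text describes patients of 13 to 17 (9.1.2), and entry is only through HCP lists (8.2.2). *Keeping it above 0:* no age floor is written (8.2.2, 8.2.4), HCPs are to recruit consecutive patients with random selection from their lists, and Question 2 can record an initiation age under 13.

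**5. Dose.** The endpoint concerns starting dose. The dose variable in 8.3 is the most recent dose, which can differ from it. The visible text supplies starting dose only as the HCP's reported usual practice (7.2.1). Table 7 in 8.3 lists age and dose only as knowledge items, so it holds no breach metric.

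**The case against.** The strongest reply is that nothing is hidden. Section 8.6 says openly that a control is impossible and that outcomes are not related to tool use. Section 3.9 already plans descriptive statistics with 95% intervals. The abstract's objective 4 speaks only of minimising inappropriate starting dose and age, without the word effect. The detailed analysis sections and the questionnaires are withheld from this public version. All of this is true, and it makes the repair easy. It does not save the endpoint as worded: a disclosed limitation that contradicts a primary endpoint still contradicts it, and no withheld analysis can supply the missing comparator.

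A reader might go further and infer that surveyed patients are 13 or older by definition, so that a favourable result is built in. The documents do not support that. No patient age criterion appears, the consent sentence explains why parental consent is needed and is not an eligibility rule, and the wording in 8.3 defines HCP experience only. HCPs are also asked about minimum age (7.2.1; Table 5 in 8.1), by an item whose text cannot be seen. An age restriction would in any case not prevent dose breaches from being reported.

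Nor does the statement in 7.2.1 that only four of the five evaluation levels are studied settle the matter. The abstract places starting dose and age with behaviours, which are among the four.

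**Conclusion.** The concern holds in this form. Endpoint 4 and objective 5 claim an effect of the tools that the design cannot estimate, and 8.6 says as much. This conclusion needs no numerical assumption. The age data are likely, but not certain, to understate breaches. The size of the understatement depends on r, which the documents do not allow anyone to estimate. The dose half has a separate fault: the variable defined in 8.3 does not match the dose named in the endpoint.

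The 2.4% limit is an illustration. It assumes no breach among 150 respondents, each standing for a different, independent patient, although 8.2.2 allows up to three patients or caregivers per HCP. Because the wording governs what may be concluded to the regulator on a primary endpoint, it should be changed before data collection.

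**What to change.** 1. **Restate endpoint 4 and objective 5 as descriptive.** Report the proportion of HCPs whose usual starting dose is above the labelled limit and the proportion of patients below the labelled minimum age at initiation, each with an exact 95% confidence interval. Drop any claim of an effect of the tools and attach the 8.6 limitations to the result. Align 7.2.1 with this wording.
2. **Reconcile 8.2.2, 8.2.4, 8.3 and 9.1.2 on age.** State that patients treated for this condition are listed whatever their age at initiation. Ask HCPs for anonymous counts by age at initiation, without the 13-and-older restriction, and make these the main source for the age proportion. Where one HCP contributes several patients, allow for clustering or say that the interval ignores it.
3. **Define a starting-dose variable in 8.3** beside the most-recent-dose variable. HCPs' usual dose supports a proportion of HCPs. A proportion of treatment starts would need starting dose per patient.

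The cost is one or two added questionnaire items and a more modest endpoint, with no extra participants.
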